#### **1.1.4.2 Adjuvant Therapy with an mTOR Inhibitor**

The Akt/mTOR pathway is activated in the great majority of SCCHN. Expression of eIF4E is functionally active in SCCHN through activation of the Akt/mTOR signaling pathway. Moreover, activation of eIF4E in histologically tumor-free surgical margins appears to be an independent predictor of recurrence. Patients with advanced stage SCCHN have a high rate of recurrence after curative intent therapy. In a preclinical model of minimal residual SCCHN, mTOR inhibitors have been shown to inhibit tumor formation and increase survival. An exploratory biomarker trial with temsirolimus in newly diagnosed advanced stage SCCHN patients showed inhibition of the Akt/mTOR pathway in tumors and PBMCs (surrogate markers) and proapoptotic activity of temsirolimus in patients with head and neck tumors.

There are data regarding long term toxicities of mTOR inhibitors. Analysis of special populations such as renal transplant patients and patients with tuberous sclerosis suggests that sirolimus and its analogues are well tolerated. Studies in renal-transplant patients have always administered sirolimus in combination with cyclosporine and/or corticosteroids making interpretation of these data regarding single agent sirolimus difficult. Nonetheless, the studies suggest that adding sirolimus to allograft rejection prophylaxis regimens is safe and does not increase immunosuppression or rate of second malignancies. Moreover, no increased incidence of immunosuppression has been observed in multiple trials of single-agent rapamycin or rapamycin analogues in cancer patients. However, the most relevant experience to this study is a trial in patients with tuberous sclerosis or sporadic lymphangioleiomyomatosis who received single-agent sirolimus for one year and had serum drug levels equal to or exceeding those in transplant patients. The most common adverse events attributable to sirolimus included aphthous ulcers and diarrhea. Twenty-five subjects entered the study and 20 were able to complete 1 year of therapy. Of the 5 subjects that

withdrew prior to completing planned therapy, only 1 did so secondary to adverse effects of sirolimus.

Therefore, the Akt/mTOR pathway is active in SCCHN, mTOR inhibitors display biologic activity in preclinical and clinical SCCHN models, and currently available oral mTOR inhibitors appear to be well tolerated even for prolonged periods of time. Taken together and given the ability to identify patients who have no evidence of disease after therapy but a high risk of recurrence, we propose studying everolimus as adjuvant therapy in this setting.

## 2 Study objectives

### Primary

Two-year progression-free survival (PFS) probability in subjects treated with everolimus versus placebo after definitive local therapy

### Secondary

- Toxicity of everolimus versus placebo as adjuvant therapy
- Site of disease progression (locoregional vs. distant) in subjects treated with everolimus versus placebo
- Incidence of second primary tumors in subjects treated with everolimus versus placebo
- Prevalence of Akt/mTOR pathway activation in locally advanced SCCHN
- Determine correlation between progression free survival (PFS) and the degree of activation of the Akt/mTOR pathway biomarkers in tumors and adjacent mucosa treated with everolimus versus placebo
- Determine if PTEN status is predictive marker of Everolimus sensitivity

## 3 Investigational plan

### 3.1 Overall study design

This is a randomized, double-blind, phase 2 study of everolimus versus placebo. Randomization will be stratified for disease stage and type of local therapy (IVa surgical vs. IVa non-surgical vs. IVb) as well as treating institution. Eight to 16 weeks after completion of definitive, curative-intent therapy for locally advanced SCCHN, potentially eligible subjects will be consented and randomized to receive either everolimus or placebo for a maximum of 1 year. Subjects will be evaluated prior to starting therapy; 4, 16, 32 and 52 weeks after starting therapy; and then at least every 4 months for a minimum of 2 years (those enrolled early will be followed for 3 years).

Radiographic assessments (CT, PET-CT, PET and/or MRI) will be conducted prior to initiating therapy and every 4-6 months for 2 years then every 6 months in year 3. Not all patients will be followed for 3 years at end of study. Minimum radiographic follow-up will be 2 years for all patients. For those subjects enrolled early, longer follow-up will determine secondary endpoints such as PFS and OS.

### 3.2 Study population

#### 3.2.1 Patient population

160 subjects (80 per arm, everolimus vs. placebo)

### 3.2.2 Inclusion and exclusion criteria

Patients must have baseline evaluations performed prior to the first dose of study drug and must meet all inclusion and exclusion criteria. Results of all baseline evaluations, which assure that all inclusion and exclusion criteria have been satisfied, must be reviewed by the Principal Investigator or his/her designee prior to enrollment of that patient. In addition, the patient must be thoroughly informed about all aspects of the study, including the study visit schedule and required evaluations and all regulatory requirements for informed consent. The written informed consent must be obtained from the patient prior to enrollment. The following criteria apply to all patients enrolled onto the study unless otherwise specified.

#### Inclusion criteria

- Squamous cell carcinoma of the head and neck that is pathologically confirmed
- Patients must have no evidence of disease (NED) within 16 weeks after receiving curative intent therapy for locally advanced squamous cell carcinoma of the head and neck (SCCHN).
  - NED is defined as ANY of the following:
    - Biopsy demonstrating no cancer cells
    - Radiographic studies (CT, MRI, or PET) demonstrating complete response or absence of cancer as judged by the investigator
    - Clinical assessment including direct visualization by nasopharyngolaryngoscopy demonstrating complete response
  - Initial TNM stage IVa or IVb (AJCC 6th edition)
  - Tumor tissue available for correlative analyses (see Section 3.4.7). Patient can be registered, randomized, and start therapy prior to specimen shipment.
  - Primary tumor site is oral cavity, oropharynx, hypopharynx, or larynx (including supraglottis and subglottis)
  - For oropharynx cancer patients only:
    - Human papilloma virus negative by in-situ hybridization, polymerase chain reaction, or negative p16 immunohistochemistry
    - Human papilloma virus positive with a history of tobacco use. Minimal tobacco exposure must be 10 pack years (pack years = average number of packs smoked per day multiplied by number of years smoked)
  - Age  $\geq$  18 years
  - Karnofsky performance status  $> 70\%$
  - Adequate bone marrow function as shown by: ANC  $\geq 1.5 \times 10^9/L$ , Platelets  $\geq 100 \times 10^9/L$ , Hb  $> 9 \text{ g/dL}$
  - Adequate liver function as shown by:
    - serum bilirubin  $\leq 1.5 \times \text{ULN}$
    - ALT and AST  $\leq 2.5 \times \text{ULN}$
  - INR and PTT  $\leq 1.5$ . (Anticoagulation is allowed if target INR  $\leq 1.5$  on a stable dose of warfarin or on a stable dose of LMW heparin for  $> 2$  weeks at time of randomization.)
  - Adequate renal function: serum creatinine  $\leq 1.5 \times \text{ULN}$

- Fasting serum cholesterol  $\leq 300$  mg/dL OR  $\leq 7.75$  mmol/L AND fasting triglycerides  $\leq 2.5 \times$  ULN. NOTE: In case one or both of these thresholds are exceeded, the patient can only be included after initiation of appropriate lipid lowering medication and confirmation of lipid levels within acceptable criteria.
- Signed informed consent

### **Exclusion criteria**

- Patients currently receiving anticancer therapies or who have received anticancer therapies within 4 weeks of the start of study drug (including chemotherapy, radiation therapy, antibody based therapy, etc.)
- Patients, who have had a major surgery or significant traumatic injury within 4 weeks of start of study drug, patients who have not recovered from the side effects of any major surgery (defined as requiring general anesthesia)
- Patients with acute radiotherapy related mucositis and dermatitis  $>$  grade 1 (all other acute radiotherapy related toxicities  $>$  grade 1 may be eligible per sponsor discretion)
- Prior treatment with any investigational drug within the preceding 4 weeks
- Patients receiving chronic, systemic treatment with corticosteroids or another immunosuppressive agent. Topical or inhaled corticosteroids are allowed.
- Patients should not receive immunization with attenuated live vaccines within one week of study entry or during study period.
- Lip, nasopharynx, nasal cavity, paranasal sinus, salivary gland, skin, or thyroid primary tumors
- Evidence of metastatic disease
- Other malignancies within the past 3 years except for adequately treated CIS of the cervix or basal or squamous cell carcinomas of the skin
- Patients who have any severe and/or uncontrolled medical conditions or other conditions that could affect their participation in the study such as:
  - Symptomatic congestive heart failure of New York heart Association Class III or IV
  - unstable angina pectoris, symptomatic congestive heart failure, myocardial infarction within 6 months of start of study drug, serious uncontrolled cardiac arrhythmia or any other clinically significant cardiac disease
  - severely impaired lung function – if suspected, pulmonary function tests should be performed with severely impaired function defined as spirometry and DLCO that is 50% of the normal predicted value and/or  $O_2$  saturation that is 88% or less at rest on room air
  - uncontrolled diabetes as defined by fasting serum glucose  $> 1.5 \times$  ULN
  - active (acute or chronic) or uncontrolled severe infections (Note: Optimal glycemic control should be achieved before starting trial therapy.)
  - liver disease such as cirrhosis, or severe hepatic impairment (Child-Pugh class C).

- Chronic or active hepatitis B or C. Note: A detailed assessment of Hepatitis B/C medical history and risk factors must be done at screening for all patients. HBV DNA and HCV RNA PCR testing are required at screening for all patients with a positive medical history based on risk factors and/or confirmation of prior HBV/HCV infection (see Section 4.6.1.2).
- A known history of HIV seropositivity
- Impairment of gastrointestinal function or gastrointestinal disease that may significantly alter the absorption of Everolimus (e.g., ulcerative disease, uncontrolled nausea, vomiting, diarrhea, malabsorption syndrome or small bowel resection)
  - N.B.: patients are allowed to administer everolimus through a feeding tube (see Appendix A)
- Patients with an active, bleeding diathesis
- Female patients who are pregnant or breast feeding, or adults of reproductive potential who are not using effective birth control methods. Adequate contraception must be used throughout the trial by both sexes and for at least 8 weeks after the last dose of study drug, by both sexes. Hormonal contraceptives are not acceptable as a sole method of contraception. (Women of childbearing potential must have a negative urine or serum pregnancy test within 7 days prior to administration of Everolimus)
- Male patient whose sexual partner(s) are WOCBP who are not willing to use adequate contraception, during the study and for 8 weeks after the end of treatment
- Patients who have received prior treatment with an mTOR inhibitor (sirolimus, temsirolimus, everolimus).
- Patients with a known hypersensitivity to Everolimus or other rapamycin analogues (sirolimus, temsirolimus) or to its excipients
- History of noncompliance to medical regimens
- Patients unwilling to or unable to comply with the protocol

### 3.2.3 Interruption or discontinuation of treatment

For patients who are unable to tolerate the protocol-specified dosing schedule, dose adjustments are permitted in order to keep the patient on study drug. If administration of Everolimus must be interrupted because of unacceptable toxicity, drug dosing will be interrupted or modified according to rules described in [Table 3-1](#). Toxicity will be assessed using the NIH-NCI Common Terminology Criteria for Adverse Events, version 4.0 (CTCAEv4.0, ([http://evs.nci.nih.gov/ftp1/CTCAE/CTCAE\\_4.03\\_2010-06-14\\_QuickReference\\_5x7.pdf](http://evs.nci.nih.gov/ftp1/CTCAE/CTCAE_4.03_2010-06-14_QuickReference_5x7.pdf))).

**Table 3.0 Everolimus dose level modification guidelines**

Dose level	Dose and schedule
0 (starting dose)	10 mg daily
-1	5 mg daily
-2	5 mg every other day

**Table 3-1 Criteria for dose-modification in case of suspected Everolimus  
Everolimus toxicity and re-initiation of Everolimus treatment**

Toxicity	Actions
Non-hematological toxicity	
Grade 2 (except pneumonitis – refer to Table 3-2)	If the toxicity is tolerable to the patient, maintain the same dose. If the toxicity is intolerable to patient, interrupt Everolimus until recovery to grade $\leq 1$ . Then reintroduce Everolimus at same dose. If event returns to grade 2, then interrupt Everolimus until recovery to grade $\leq 1$ . Then reintroduce Everolimus at the lower dose level.
Grade 3 (except hyperlipidemia*) (except pneumonitis – refer to Table 3-2)	Interrupt Everolimus until recovery to grade $\leq 1$ . Then reintroduce Everolimus at the lower dose level. For pneumonitis consider the use of a short course of corticosteroids.
Grade 4	Discontinue Everolimus.
Hematological toxicity	
Grade 2 Thrombocytopenia (platelets <math><75, \geq 50 \times 10^9/L</math>)	Interrupt Everolimus until recovery to grade $\leq 1$ ( $>75 \times 10^9/L$ ). Then reintroduce Everolimus at initial dose. If thrombocytopenia again returns to grade 2, interrupt Everolimus until recovery to grade $\leq 1$ . Then reintroduce Everolimus at the lower dose level.
Grade 3 Thrombocytopenia (platelets <math><50, \geq 25 \times 10^9/L</math>)	Interrupt Everolimus until recovery to grade $\leq 1$ (platelets $\geq 75 \times 10^9/L$ ). Then resume Everolimus at one dose level lower. If grade 3 thrombocytopenia recurs, discontinue Everolimus.
Grade 4 Thrombocytopenia (platelets <math><25 \times 10^9/L</math>)	Discontinue Everolimus.
Grade 3 Neutropenia (neutrophils <math><1, \geq 0.5 \times 10^9/L</math>)	Interrupt Everolimus until recovery to grade $\leq 1$ (neutrophils $\geq 1.5 \times 10^9/L$ ). Then resume Everolimus at the initial dose. If ANC again returns to Grade 3, hold Everolimus until the ANC $\geq 1.5 \times 10^9/L$ . Then resume Everolimus dosing at the lower dose level. Discontinue patient from study therapy for a third episode of grade 3 neutropenia.
Grade 4 Neutropenia (neutrophils <math><0.5 \times 10^9/L</math>)	Interrupt Everolimus until recovery to grade $\leq 1$ (neutrophils $\geq 1.5 \times 10^9/L$ ). Then resume Everolimus at the lower dose level. If grade 3 or grade 4 neutropenia occurs despite this dose reduction, discontinue Everolimus.
Grade 3 febrile neutropenia (not life-threatening)	Interrupt Everolimus until resolution of fever and neutropenia to grade $\leq 1$ . Hold further Everolimus until the ANC $\geq 1,500/\text{mm}^3$ and fever has resolved. Then resume Everolimus at the lower dose level. If febrile neutropenia recurs, discontinue Everolimus.
Grade 4 febrile neutropenia (life-threatening)	Discontinue Everolimus.
Any hematological or non-hematological toxicity requiring interruption for $\geq 3$ weeks	Discontinue Everolimus.

\*Grade 3 hyperlipidemia (hypercholesterolemia and/or hypertriglyceridemia) should be managed using medical therapies (see Sec. 3.2.5.2).

Subjects who require anticoagulation after randomization should be treated according to their physician's discretion and can continue on study. Since everolimus can interact with warfarin, the use of low-molecular weight heparins or non-coumarin containing anticoagulants is encouraged. If warfain is administered, close monitoring of INR is warranted.

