Physicians and patients should be aware of the increased risk of infection with everolimus. Treat pre-existing infections prior to starting treatment with everolimus. While taking everolimus, be vigilant for symptoms and signs of infection; if a diagnosis of infection is made, institute appropriate treatment promptly and consider interruption or discontinuation of everolimus. If a diagnosis of invasive systemic fungal infection is made, discontinue everolimus and treat with appropriate antifungal therapy.

Reactivation of Hepatitis B (HBV) has been observed in patients with cancer receiving chemotherapy (Yeo 2004). Sporadic cases of Hepatitis B reactivation have also been seen in this setting with everolimus. Use of antivirals during anti-cancer therapy has been shown to reduce the risk of Hepatitis B virus reactivation and associated morbidity and mortality (Loomba 2008). A detailed assessment of Hepatitis B/C medical history and risk factors must

be done for all patients at screening, with testing performed prior to the first dose of everolimus.

Hypersensitivity reactions manifested by symptoms including, but not limited to, anaphylaxis, dyspnea, flushing, chest pain or angioedema (e.g. swelling of the airways or tongue, with or without respiratory impairment) have been observed with everolimus.

Hyperglycemia has been reported in clinical trials. Monitoring of fasting serum glucose is recommended prior to the start of everolimus therapy and periodically thereafter. Optimal glycemic control should be achieved before starting a patient on everolimus. Mouth ulcers, stomatitis and oral mucositis have been seen in patients treated with everolimus. In such cases topical treatments are recommended, but alcohol- or peroxide-containing

Elevations of serum creatinine, usually mild, have been reported in clinical trials. Monitoring of renal function, including measurement of blood urea nitrogen (BUN) or serum creatinine, is recommended prior to the start of everolimus therapy and periodically thereafter.

Decreased hemoglobin, lymphocytes, platelets and neutrophils have been reported in clinical trials. Monitoring of complete blood count is recommended prior to the start of everolimus therapy and periodically thereafter.

Everolimus is not recommended in patients with severe hepatic impairment, (Child-Pugh class C).

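### Table 3-1 has no hypersensitivity exception, so as written a grade 3 reaction that settles in under 3 weeks is restarted one dose level lower; stopping is permitted but not required

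*Combined protocol and SAP*

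**What the plan says.** Section 3.2.3 allows dose adjustment for patients who cannot tolerate the schedule. When toxicity is unacceptable, "drug dosing will be interrupted or modified according to rules described in" Table 3-1.

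- **Grade 3 non-hematological row.** The exceptions are hyperlipidemia and pneumonitis. Otherwise the drug is held until grade 1 or lower, and the row continues: "Then reintroduce Everolimus at the lower dose level. For pneumonitis consider the use of a short course of corticosteroids".
- **Grade 2 non-hematological row.** The only exception is pneumonitis. A tolerable event continues at the same dose. An intolerable one is held until grade 1 or lower, with the instruction "Then reintroduce Everolimus at same dose"; the dose is lowered only if the event returns to grade 2.
- **Stops.** Grade 4, and any toxicity that needs a hold of 3 weeks or more, lead to discontinuation.
- **Dose levels (Table 3.0).** 10 mg daily, 5 mg daily, then "5 mg every other day".

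Hypersensitivity appears in two other places. Section 3.2.5 reports, as observed with everolimus, "Hypersensitivity reactions manifested by symptoms including, but not limited to, anaphylaxis, dyspnea, flushing, chest pain or angioedema", and gives airway swelling as an example; no dosing action follows. The exclusion criteria in section 3.2.2 bar "Patients with a known hypersensitivity to Everolimus or other rapamycin analogues (sirolimus, temsirolimus) or to its excipients".

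**The concern.** Lowering the dose is a reasonable response to most everolimus toxicities, and the generic rows are written for those. Hypersensitivity differs: the entry criterion treats a known history as disqualifying and sets no dose below which exposure is acceptable. A patient who has a grade 3 reaction on study acquires that history, yet the row that then applies directs a restart at a lower dose.

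What is at stake is patient safety. These patients have no evidence of disease, and section 1.1.4.1 says that routine management at this point includes no active treatment. In a multicenter trial, a missing rule also means that the same reaction may be handled differently from site to site.

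**Working it through.** **Tracing the rule.** No figure in the plan needs reproducing for this part; the texts are set side by side.

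1. Section 3.2.3 routes the event to Table 3-1.
2. Hypersensitivity is non-hematological and is not among the exceptions, so the generic rows apply.
3. Grade 3, hold under 3 weeks: recover to grade 1 or lower, then restart at 5 mg daily if the patient was on 10 mg, or at 5 mg every other day if on 5 mg daily.
4. Grade 2, intolerable, first occurrence: restart at the same dose.
5. Grade 4, or a hold of 3 weeks or more: stop.
6. Sections 3.2.2 to 3.2.5, 3.3.1, 3.4.4 and 4.6 contain no on-treatment stop for hypersensitivity. Section 3.2.5 does order discontinuation for invasive systemic fungal infection, so the protocol gives event-specific stops where it intends them.

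**How many patients.** The documents give neither a rate nor a grade split. For illustration only, assume that 0.1% to 1% of the 80 everolimus patients have a grade 3 reaction that settles in under 3 weeks.

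- Expected number: 80 × 0.001 = 0.08, to 80 × 0.01 = 0.8.
- Chance of at least one: 1 − 0.999^80 = 0.077, to 1 − 0.99^80 = 0.552.

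This counts patients who reach the restart row. Fewer would be rechallenged, because investigators may stop.

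**What a mandatory stop could cost.** Inputs from section 6.1, Sample Size: 2-year PFS of 50% and 70%, exponential survival, 36 months of uniform accrual, 24 months of follow-up, 66 per arm, two-sided 0.05.

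- Hazards per month: λ = −ln(S)/24, so 0.02888 (placebo) and 0.01486 (everolimus); HR = 1.94, as the plan states.
- Event probability: 1 − [exp(−24λ) − exp(−60λ)]/(36λ) = 0.689 and 0.458.
- Events: 66 × (0.689 + 0.458) = 75.7.
- Power: Φ(ln HR × √(events/4) − 1.96) = Φ(0.930) = 0.824, against the plan's 80%.

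Now assume that k of 80 everolimus patients stop on day 1 and carry placebo risk from then on, and treat the arm as exponential at the mixed 2-year PFS, (1 − k/80) × 70% + (k/80) × 50%:

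| k | 2-year PFS | HR | Power at N=132 |
|---|---|---|---|
| 0 | 70.0% | 1.94 | 0.824 |
| 1 | 69.75% | 1.92 | 0.814 |
| 2 | 69.5% | 1.91 | 0.803 |
| 4 | 69.0% | 1.87 | 0.780 |

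Stops on placebo do not change PFS risk. Later stops, or a partial loss of benefit, cost less than the table shows.

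**The case against.** The strongest reply is that the protocol already lets the investigator stop. Section 3.2.5 calls Table 3-1 general recommendations, section 3.3.1 ends treatment at unacceptable toxicity, and section 3.4.4.1 includes discontinuation among the ways to treat an adverse event. The entry exclusion itself signals that hypersensitivity is disqualifying. The gravest reactions, at grade 4, already stop treatment; section 3.2.4 adds weekly follow-up, and section 4.6 adds Principal Investigator recommendations after a serious event. The renal cancer safety data in section 3.2.5 (274 patients on everolimus) do not list hypersensitivity among the common reactions or the leading grade 3-4 ones, which supports calling it uncommon. The Investigator's Brochure, which is not part of these documents, may give guidance.

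Most of this stands. It lowers the likelihood of re-exposure, and it rules out the inference that an investigator who stops after a grade 3 reaction departs from the protocol. It does not supply a requirement to stop: section 3.2.3 speaks of rules, and the row that applies says restart.

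A reader might also infer more from the recurrence instructions, since two hematological rows say "If grade 3 thrombocytopenia recurs, discontinue Everolimus" and "If febrile neutropenia recurs, discontinue Everolimus" while the grade 3 non-hematological row is silent. That contrast does not help. The silence applies to every grade 3 toxicity in that row, and the grade 3 neutropenia row allows two restarts before stopping at the third episode. Nor are restarts limited only by the lowest dose level: grade 4, the 3-week limit and unacceptable toxicity end them too.

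**Conclusion.** The point holds for grade 3. As written, Table 3-1 directs a lower-dose restart after a suspected grade 3 hypersensitivity reaction that settles in under 3 weeks, for a risk that the protocol names and screens out at entry, and no section requires a stop. The gap is a missing mandatory stop, not a ban on stopping. The grade 2 same-dose restart is a secondary matter of wording.

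A reader might infer that the entry exclusion contradicts Table 3-1. It does not, because it governs eligibility only; it shows how the protocol regards the risk. A reader might also infer a threat to the trial's result. There is none: the primary analysis is not affected.

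The number of patients affected is unknown and probably small. The range of 0.08 to 0.8 expected patients rests wholly on the assumed rate of 0.1% to 1%. The change is worth making because the re-exposure is foreseeable and avoidable, and the rule costs little.

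**What to change.** 1. Add hypersensitivity to the exceptions in the grade 3 non-hematological row of Table 3-1.
2. State in section 3.2.5 that blinded study drug is permanently discontinued, without rechallenge, for any hypersensitivity reaction of grade 3 or higher suspected to be related to study drug, and for anaphylaxis or angioedema of any grade.
3. State that this ends study drug only: the patient stays in follow-up for progression and survival and in the analysis, and no unblinding is required. This needs saying because section 3.2.4 and the pneumonitis table speak of leaving the study.
4. As a secondary clarification, exempt a grade 2 event that the investigator judges to be hypersensitivity from the automatic same-dose restart, and leave rechallenge or discontinuation to the investigator. No permanent stop is proposed at grade 2 beyond anaphylaxis and angioedema, because rash, pruritus and dyspnoea are common on everolimus (section 3.2.5).

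The cost is an exception in two table rows and a short statement in section 3.2.5, with no added procedures or patients. The downside is that a few patients in either arm, some with misattributed events, stop early. On the assumptions above, the stops (1 to 4 on everolimus) could outnumber the true grade 3 reactions that the rule is meant to catch; even so, the worst case leaves power at 78%.
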